4.7 Informed Consent Process

4.7.1 General process

Prior to enrolling in the clinical study and conducting study-specific procedures, all subjects will be consented, as required by applicable regulations and the center's Institutional Review Board (IRB)/Ethics Committee (EC). Informed consent must be obtained from each subject prior to any study related procedures. The consent form must be signed and dated by the subject and by the person obtaining the consent.

The principal investigator or his/her authorized designee will conduct the Informed Consent Process. This process will include a verbal discussion with the subject on all aspects of the clinical study that are relevant to the subject's decision to participate in the clinical study.

The subject shall be provided with the informed consent form that is written in a language that is understandable to the subject and has been approved by the center's IRB/EC. Failure to obtain informed consent from a subject prior to study enrollment should be reported to St. Jude Medical within 5 working days and to the reviewing center's IRB/EC/ consistent with the center's IRB/EC reporting requirements.

5.0 DEVICE UNDER INVESTIGATION AND CONTROL/COMPARATORS (IF APPLICABLE)

5.1 Device Description

All subjects will be implanted with a regulatory approved (CE marked and Market released) St. Jude Medical CRT device compatible with MultiPoint™ Pacing feature [REDACTED] or any other St Jude Medical (SJM) model compatible with the MPP algorithm) and St. Jude Medical quadripolar left ventricular lead [REDACTED]

During the follow-ups, implanted devices will be checked with [REDACTED] programmer.

Any commercially available and regulatory approved right atrial and right ventricular leads can be used in this investigation.

All of the devices used in this investigation, have received appropriate regulatory certification and are market released.

ST. JUDE MEDICAL™

Study Document No: SJM-CIP-10058 Ver. A

Study Name: QUARTO III study

CIP

5.2 Device Handling & Storage

St. Jude Medical requires all investigational products be stored, according to the labeling, in a secure area to prevent unauthorized access or use. This will prevent non-investigational use of products that are provided for this study.

6.0 PROCEDURES

6.1 Study Flow Chart

[figure not shown]

Figure 1: Flow Chart

**CIP****6.2 Procedures**

The clinical study will be conducted in accordance with the CIP. All parties participating in the conduct of the clinical study will be qualified by education, training, or experience to perform their tasks and this training will be documented appropriately. The clinical study will not commence until St. Jude Medical receives written approval from the IRB/EC and relevant regulatory authorities and all required documents have been collected from the site(s).

All the mandatory procedures are listed in the following tables and detailed in the next pages:

Study Activity \ Visit	Enrollment Visit	Baseline visit	Implant Visit (within 7 days)	Substudy visit* (within 7 days of implant)	Unscheduled FU	6M Follow Up (+/- 30 days)
Patient Informed Consent Process	X					
Inc/Exc criteria	X					
Patient Data and Medical History		X				
Current Cardiac Medication		X			(X)	X
NYHA Class Evaluation		X			(X)	X
Core Lab Echocardiography		X			(X)	X
Implant Procedure Details			X			
MPP Vector Test			X		(X)	
Conduction Delays Test			X		(X)	X
Device Interrogation and Programming			X		(X)	X
MPP Programming			X		X	(X)
Fluoroscopy Images			X			
Substudy Inc/Exc criteria*				X		
Substudy Echocardiography*				X		
Adverse Event	(X)	(X)	(X)	(X)	(X)	(X)
Hospitalization	(X)	(X)	(X)	(X)	(X)	(X)
Protocol Deviation	(X)	(X)	(X)	(X)	(X)	(X)
Withdrawal	(X)	(X)	(X)	(X)	(X)	(X)
Death	(X)	(X)	(X)	(X)	(X)	(X)

*Only for selected Sites; (X) if applicable

Table 1: List of all study specific activities/procedures

The Case Report Forms used to complete all the information detailed above are summarized in the table below:

Visit CRFs	Baseline Visit	Implant Visit	Substudy Visit* (within 7 days implant)	Unscheduled	6 Month (+/-30 days)
Enrollment Form	X	-	-	-	-
Baseline Form	X	-	-	-	-
Implant Form	-	X	-	-	-
Substudy Enrollment Form*	-	-	X	-	-
Substudy Echo Form*	-	-	X	-	-
Follow Up Form	-	-	-	(X)	X
Deviation Form	(X)	(X)	(X)	(X)	(X)
Adverse Event Form	(X)	(X)	(X)	(X)	(X)
Hospitalization Form	(X)	(X)	(X)	(X)	(X)
System Revision Form	(X)	(X)	(X)	(X)	(X)
Withdrawal Form	(X)	(X)	(X)	(X)	(X)
Death Form	(X)	(X)	(X)	(X)	(X)

*Only for selected sites; (X) if applicable

Table 2: Case Report Forms (CRF)

Informed Consent Procedure and Inclusion/Exclusion Criteria check:

Patient's eligibility criteria and Informed consent Procedure is performed before any study related activity.

Patient Data and Medical History:

Subject's demographic data will be collected at the Baseline Visit together with cardiomyopathy etiology, implant indication and co-morbidities.

Current Cardiac Medication

The current cardiac medications will be collected at Baseline, while during the Follow-up Visits only the changes will be documented.

NYHA Class Evaluation

The patient's New York Heart Association class will be assessed at Baseline and during all Follow-up visits.

Implant Procedure Details

Implant Procedure details (standard CRT-D implant) will be collected at Implant visit.

Indicate model n°, serial n° and date of implant of entire implanted system (CRT-D device, Right Atrial (RA) lead, RV lead and LV lead).

Final positions of all the implanted leads must be specified: right atrium, right ventricle and left ventricle lead positions. Additionally the final position of the LV poles will be collected.

Fluoroscopy Images Collection (EDC upload)

As the lead placement is important to understanding the patient's response to CRT-D, two Fluoroscopy images are requested to be collected:

- LAO (Left Anterior Oblique, $45^\circ \pm 10^\circ$) (mandatory)
- RAO (Right Anterior Oblique, $45^\circ \pm 10^\circ$) (mandatory)
- AP (Anterior - Posterior) If available

The position of all leads must be clearly visible to allow matching with the venous anatomy. These anonymized images should be uploaded to the Electronic Data Capture (EDC) system .

MPP Vector Test

In order to allow future activation of MPP, specific LV pacing capture thresholds and Phrenic Nerve Stimulation (PNS) tests must be performed for the 4 cathodes during the implant.

The test is considered positive in case is possible to identify at least 2 vectors from different Groups (with different Cathodes) [REDACTED]

Conduction Delays Test

The conduction delays between right and left ventricle will be performed during Implant and at 6 Month follow up (with RV paced). [REDACTED] and will end in about one minute. [REDACTED]

Device Interrogation and Programming

Device will be interrogated and all the diagnostics retrieved. Standard sensing, pacing and impedance measurements will be performed for all implanted leads at implant and each in-clinic follow-up.

The recommendation for the MPP programming in this study are (see Appendix E. Guidelines):

MPP feature: MPP feature will be TURNED ON in all patients with positive MPP Vector Test at implant. If the Investigator decides not to turn ON the MPP feature or there are not enough vectors available to activate this feature, the patient will be excluded from the study.

MPP Cathode Selection: The pacing configuration will be chosen by the investigator following one of the 2 different approaches:

- Electrical approach: choose the most electrically separated vectors based on the data provided [REDACTED]
- Anatomical approach: choose the most anatomically separated vectors based on the position of each pole, documented through fluoroscopic images.

**CIP**

In this study, the Electrical approach is recommended. According the results of the Conduction Delays Test (with RV Paced) LV1 should be the one with the shortest conduction time, and LV2 the one with the longest conduction time.

Pacing Vectors Selection: The anode of the pacing configuration will be chosen by the investigator based on the results of the capture threshold and PNS obtained in the MPP Vector Test.

MPP delays programming: In this study the following general MPP programming is recommended:

- MPP pacing sequence: LV first: LV1 $\xrightarrow{D1}$ LV2 $\xrightarrow{D2}$ RV
- Timing Delays: use the minimum delays of 5 ms between LV1-LV2 and LV2-RV.

**Echocardiography (Core Lab)**

Echocardiography images will be obtained according to the Echo Protocol at Baseline and 6 Month visit. They will be submitted to an independent Echo Core Lab for central evaluation and assessment.

The Baseline Echocardiography will be performed at any time after the patient signs the Patient Informed Consent, within 7 days before and 48 hours after the CRT-D implant procedure (with the CRT-D in No Pacing). The 6 Month Echocardiography will be performed during the 6 Month visit.

The Echocardiography must be recorded in DICOM format and sent/uploaded to the Echo Core Lab within 72 hours (3 working days). The Core Lab will analyze the Baseline and the 6 Month Echocardiography and provide the evaluation of the CRT response based on the LVESV reduction. In addition, the following data will be analyzed and measured by the Core Lab:

- LVEDD and LVESD
- LVEDV and LVESV
- LVEF

CIP

- Mitral Insufficiency
- Dyssynchrony measured by the strain rate (speckle tracking echocardiography) between the anteroseptal segment and the posterior wall (in patients which it is available)

Substudy Echocardiography

An additional Echocardiography will be obtained at the Substudy Visit according to the Echo Protocol. It will be recorded in DICOM and RAW file. This Echocardiography will not be sent/uploaded to the Echo Core Lab but evaluated locally at hospital. The following substudy data will be measured and collected at site:

- Left Ventricular Outflow Tract (LVOT) diameter (although only one measure is mandatory, 3 measurements are recommended)
- Cardiac Output (CO) by Velocity Time Integral (VTI) value under 5 different pacing methods:
 - No Pacing
 - MPP using Electrical approach: choose the most electrically separated vectors (LV1 and LV2) based on the data provided by [REDACTED] and PNS obtained in the MPP Vector Test.
 - MPP using Anatomical approach: choose the most anatomically separated vectors (LV1 and LV2) based on the position of each pole (documented through fluoroscopic images) and the capture threshold and PNS obtained in the MPP Vector Test.
 - SPP: choose the vectors LV1 and LV2 of the approach (Electrical or Anatomical) with the best CO, and measure the data in:
 - SPP with LV1
 - SPP with LV2

6.3 Enrollment Visit

The Enrollment will be performed within 7 days before the Implant Procedure. The following enrollment activities are performed after the subject has been screened and must occur before any study procedure/visit.

- The principal or delegated study personnel are responsible for screening all potential subjects to determine subject eligibility for the study.
- If a patient meets all inclusion criteria and does not meet any of the exclusion criteria, he/she is eligible for the investigation.
- Inform the eligible patient verbally about the investigation and provide the information sheet and consent form to the patient.
- Provide ample time to the patient to read and understand the information sheet and consent form and to consider participation in the clinical investigation.
- Obtain the signature and date from the eligible patient on the Ethics Committee (EC) approved informed consent form.

CIP

- If an eligible patient does not sign and date the informed consent form, he cannot participate in the investigation. No further protocol required activities are performed.
- Obtain the signature and date from the principal or delegated investigator on the EC approved consent form.
- The subject is enrolled in the investigation when the patient signs the EC approved consent form.
- Provide one original signed version of the informed consent form to the subject (signed by both subject and investigator)
- File second original signed version of the informed consent form in the Investigator Site Binder (ISB).
- Record enrollment information (name of the study, date of consent and Inclusion/exclusion information) in the hospital records and complete and submit the Enrollment form in a timely manner (recommended within 5 days)
- Notification of enrollment to the sponsor will take place only when the sponsor receives the enrollment form

NOTE: As soon as the subject signs the Patient Informed Consent, adverse events need to be reported according to the guidelines mentioned in section 8.2

If a subject does not meet all inclusion criteria or meets any of the exclusion criteria, the subject cannot participate in the study and cannot be enrolled.

In case the subject was already consented to participate in the study, but does not meet inclusion/exclusion criteria, the following actions will be taken:

- Document enrollment information (name of the study, date of consent and inclusion/exclusion) in the hospital records; complete the Enrollment and Termination Forms. The forms must be authorized/approved by the principal or delegated investigator.
- Inform the subject about the Termination.
- Refer to Table 2: “Case Report Forms”.
- Complete study deviation for inclusion/exclusion not met.
- The Ethics Committee (EC) should be notify appropriately about any deviation with regards to obtaining the informed consent

6.4 Baseline Visit (within 7 days of Enrollment)

The clinical data collection of the Baseline Visit will be performed after patient signs the Patient Informed Consent and within 7 days after the Enrollment visit. The following information will be collected to describe patient’s clinical status:

- Patient Data and Medical History
- Current Cardiac Medication
- NYHA Class Evaluation

**CIP**

- Core Lab Echocardiography
- Adverse Events and/or Hospitalization and/or Death and/or Protocol Deviation notification (if applicable)

A Baseline Core Lab Echocardiography will be performed at any time after the patient signs the Patient Informed Consent, within 7 days before and 48 hours after the CRT-D implant procedure (with the CRT-D in No Pacing).

The center must record the Echocardiography in DICOM format and send/provide it to the Core Lab within 72 hours (3 working days). The Core Lab will analyze the Echocardiography received and provide the evaluation of the measurements to St Jude Medical.

6.5 Implant visit (within 7 days of Enrollment)

The implant procedure of a SJM MPP compatible CRT-D system will be implanted with standard procedure within 7 days after the Enrollment.

The Implant Procedures Details will be collected at the Implant section:

- System information, model number, serial number and date of implant of entire implanted system (device, RA lead, RV lead and LV lead)
- Leads position and LV lead poles position
- Adverse Events and/or Hospitalization and/or Death and/or Protocol Deviation notification (if applicable)
- Fluoroscopy Images collection (EDC upload)

The following device tests will be collected at the Implant section:

- MPP Vector Test
- Conduction Delays Test
- MPP programming (ON)
- Final MPP configurations and method followed to decide it (Electrical delay approach or Anatomical approach)

There are no specific procedures to be done for the substudy patients.

6.6 Substudy Visit (within 7 days of the Implant)

For the patients participating in the substudy a Hospital Echocardiography will be performed within 7 days of the Implant procedure. Only patients in sinus rhythm in the moment of the Echocardiography can participate in this substudy.

The substudy data detailed in Section 6.0 Hospital Echocardiography will be measured and collected at site. This Echocardiography will not be sent/uploaded to the Echo Core Lab

**6.7 Six Month Follow-up visit (In Clinic, 180 days +/- 30 days from device implant)**

The 6 Month Follow-up visit must be performed in-clinic within 180 +/- 30 days from the implant procedure. The purpose of the 6 Month Follow-Up visit is to check the patient's and CRT-D system's status as well as collect the necessary data to satisfy the study endpoints.

The following information will be collected:

- Current Cardiac Medication
- NYHA Class evaluation
- Echocardiography (Core Lab)
- Device interrogation and Programming
- Adverse Events and/or Hospitalization and/or Death and/or Protocol Deviation notification (if applicable)

The center must record the Echocardiography in DICOM format and send/provide it to the Echo Core Lab within 72 hours (3 working days). The Core Lab will analyze the Echocardiography received and provide the evaluation of the measurements to St Jude Medical

The Core Lab will be the responsible of classifying the patients as responders or non-responders according to the result of the analysis of the material provided.

At the 6 Month visit the MPP programming will be according investigator's discretion.

There are no specific procedures to be done for the substudy patients.

6.8 Unscheduled Visits (In Clinic)

If there is any change in the MPP programming an Unscheduled Follow-up Form should be completed. No specific activity is forecasted for this visit, however the center should document all of the following whenever applicable:

- Any changes in Current Cardiac Medication
- Any changes in NYHA Class
- MPP Vector Test
- Conduction Delays Test (if available)
- Any changes made to the MPP programming
- Any Adverse Events and/or Hospitalization and/or Death and/or Protocol Deviation notification

6.9 Description of activities performed by Sponsor Representatives

Trained sponsor personnel may perform certain activities to ensure compliance to the investigational plan and provide technical expertise.

CIP

Sponsor personnel may:

- Provide technical support to the Investigators during device tests and programming
- Review medical charts to ensure accurate reporting of data in the electronic CRF (eCRF)

Sponsor personnel will not:

- Perform the informed consent process
- Practice medicine
- Provide medical diagnosis or treatment to subjects
- Discuss a subject's condition or treatment with a subject without the approval and presence of a health care practitioner
- Independently collect clinical investigational data
- Complete or sign study's Case report Forms

6.10 Subject study completion

When the subject's participation in the clinical study has been completed which will be latest after the 6 Months FU visit the subject will return to the medical care as per physician's recommendation.

6.11 Any Known or Foreseeable Factors that May Compromise the Outcome of the Clinical Study or the Interpretation of the Results

All foreseeable factors that may compromise the outcome have been taken into account by clinical study design and well defined subject selection criteria.

It is planned to enroll approximately [REDACTED] patients in the study from around [REDACTED] centers. The inclusion will be competitive and there is not any enrollment target per center.

It will be assured at the time of enrollment that the patients are able to follow the study schedule. Sponsor personnel will support the investigators and will ensure the completion of the Follow Ups. It is expected anyway a percentage of patients who will not complete the study procedures. This figure has been taken into account for the sample size calculation.

6.12 Criteria and Procedures for Subject Withdrawal or Discontinuation

Subjects must be informed about their right to withdraw from the study at any time and for any reason without sanction, penalty or loss of benefits to which the subject is otherwise entitled and withdrawal from the study will not jeopardize their future medical care or relationship with the investigator. Subjects will be asked to specify the reason for the termination, but have the right not to answer.

The investigator may decide to withdraw a subject from the study at any time with reasonable rationale. The subject's future care will not be influenced by a decision, voluntary or otherwise, to

**CIP**

withdraw from the study. All reasonable efforts should be made to retain the subject in the clinical study until completion of the study.

Reasons for subject's withdrawal include, but are not limited to:

- Subject refuses to continue participating in the study
- Subject does not meet the inclusion/exclusion criteria and does not require additional follow-up for safety reasons.
- Subject is deceased (cause must be documented)
- Subject's non-compliance
- Subject's participation is terminated by the PI or investigator, although the subject consented, since participation is no longer medically appropriate
- Subject is 'lost to follow up': Subject does not adhere to the scheduled follow up visits but has not explicitly requested to be withdrawn from the clinical study. (This does not apply to missed visits). Site personnel should at all times make all reasonable efforts to locate and communicate with the subject in order to achieve subject compliance to the scheduled follow up visits:
 1. A subject will be considered 'Lost to Follow Up' after a minimum of 2 phone calls of a physician or delegate at the investigational site to the subject or contact. These 2 phone calls need to be documented in the subject's hospital records.
 2. If these attempts are unsuccessful, a letter should be sent to the subject's last known address or general practitioner (GP) and a copy of this letter should be maintained in the subject's hospital records.

Note: If a subject misses one or more of the scheduled follow up visits (inclusive of the assigned visit windows), this will be considered as a missed visit. The subject may therefore still return for subsequent visits and will not be excluded from the study.

If a subject withdraws from the clinical study, the site will record the subject's reasons for withdrawal, on a Termination CRF.

When subject withdrawal from the clinical study is due to an adverse event the subject will be followed until resolution of that adverse event or determination that the subject's condition is stable. The status of the subject's condition should be documented at the time of withdrawal.

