Design:	
The investigation is a post-marketing, prospective, multicenter, regional, and non-randomized study.
 
Data will be collected at Enrollment, Baseline, Implant, Unscheduled visits and 6 Month Follow-Up. Patients will exit the study after a completed 6 Month Follow-Up Visit.
 
During the Enrollment visit, the Inclusion/Exclusion criteria will be verified and the Informed Consent Procedure will be performed. Patients will start their participation in the study once they sign the Informed Consent, prior to the CRT-D implantation.
 
During the Baseline visit, demographic data, medical history, and cardiovascular medication will be collected. Echocardiography measurements will be collected following the Echo protocol and will be evaluated by an Echo Core Lab. At Implant procedure, the procedure details will be collected and the MPP feature will be turned ON.
 
During the 6 Month visit, clinical and Echocardiography data will be collected. The Echo Core Lab will analyze the data to assess the percentage of responder and non-responder patients, according to LVESV reduction.
 
The total duration of the study is expected to be approximately [REDACTED] years with about [REDACTED] years of enrollment and 6 months of Follow-up for the last patient enrolled.
 
[REDACTED]
 
Approximately [REDACTED] subjects will be enrolled in this study.

CIP

Devices used:	
All subjects will be implanted with a CE-approved St. Jude Medical CRT-D device compatible with MultiPoint™ Pacing feature (models n° [REDACTED] or any other St Jude Medical model compatible with the MPP algorithm) and St. Jude Medical quadripolar left ventricular lead [REDACTED]. Future devices with MPP feature may be added once are market release.
 
All of the devices used in this investigation have received appropriate regulatory certification (are CE marked and market released).

Study Population	
Patients meeting all the Inclusion and none of the Exclusion criteria will be fully informed about the investigation and asked to participate in the investigation. In case the patient agrees, a duly signed and dated Patient Informed Consent form will be obtained.
 
A patient becomes a subject once he/she has been fully informed about the study, has agreed to participate, signed & dated the consent.

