4.4.2 Secondary Endpoint

The secondary endpoints of this study are:

- Reverse LV remodeling, measured as changes in LVESV, Left Ventricular End Diastolic Volume (LVEDV), Left Ventricular End Systolic Diameter (LVESD), Left Ventricular End Diastolic Diameter (LVEDD) and Left Ventricular Ejection Fraction (LVEF) at 6 months with MPP compared with no pacing at Baseline
 - Comparison of the above mentioned echo parameters with the patient cohort stratified by etiology (ischemic versus non ischemic patients)
- Percentage of super-responders** at 6 months in MPP
- Dyssynchrony measured by the strain rate (speckle tracking echocardiography) between the anteroseptal segment and the posterior wall (if available)

CIP

- LV lead position
 - Short axis (posteriorolateral, lateral, anterolateral)
 - Long axis (apical, mid-ventricular, basal)
- NYHA class changes at 6 months
- All-cause mortality at 6 months
- All-cause, cardiovascular and/or heart failure hospitalization rate at 6 months
- Combined endpoint of mortality and heart failure hospitalization at 6 months
- Combined endpoint of mortality and cardiovascular hospitalization at 6 months

**Super-responder is defined as a patient with a mean absolute LVEF increase of >14% at 6 months post-implant compared with No Pacing at Baseline.

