8.1.5.2 Anticipated Serious Adverse Device Effect (ASADE)

A serious adverse device effect which by its nature, incidence, severity or outcome has been previously identified in the risk analysis report.

8.2 Procedure for assessing, recording and reporting adverse events, adverse device effects, serious adverse events and serious adverse device effects:

Safety surveillance within this study and the safety reporting both performed by the investigator, starts as soon as the subject is enrolled in this study (date of signature of the informed consent). The safety surveillance and the safety reporting will continue until the last investigational visit has been performed, the subject is deceased, the subject/investigator concludes his participation into the study or the subject/investigator withdraws the subject from the study, except as otherwise specified in the CIP.

All adverse event data including deaths will be collected throughout the clinical study and will be reported to the Sponsor through the EDC system. The Investigator will record all adverse events and device deficiencies on the appropriate case report forms.

Records relating to the subject's subsequent medical course must be maintained and submitted (as applicable) to the Sponsor until the event has subsided or, in case of permanent impairment, until the event stabilizes and the overall clinical outcome has been ascertained. Adverse events will be monitored until they are adequately resolved. The status of the subject's condition should be documented at each visit.

The investigator will report the event to the IRB/EC per their reporting requirements.

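### Six-month mortality and hospitalisation are not assured to day 180 for subjects who miss the only scheduled follow-up visit or attend it before day 180

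*Combined protocol and SAP*

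**What the plan says.** **Visits and exit.** The Synopsis (Design) lists the collection points: "Data will be collected at Enrollment, Baseline, Implant, Unscheduled visits and 6 Month Follow-Up". Section 6.7 sets the window: "The 6 Month Follow-up visit must be performed in-clinic within 180 +/- 30 days from the implant procedure". The Synopsis adds: "Patients will exit the study after a completed 6 Month Follow-Up Visit". Table 1 in section 6.2 shows no other scheduled post-implant visit for all subjects; the substudy visit within 7 days of implant applies to selected sites only.

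**Surveillance.** Section 8.2 states: "The safety surveillance and the safety reporting will continue until the last investigational visit has been performed". Its other end points are death, conclusion of participation and withdrawal.

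**Non-attendance.** Section 6.12 defines lost to follow-up as failure to keep scheduled visits without a request to withdraw, and adds in parentheses: "This does not apply to missed visits". Two documented calls and then a letter follow under that category. A Note then classes a scheduled visit missed beyond its window as a missed visit, and continues: "The subject may therefore still return for subsequent visits and will not be excluded from the study".

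**Endpoints.** Section 4.4.2 lists "All-cause mortality at 6 months" among the secondary endpoints, with hospitalisation rates (all-cause, cardiovascular, heart failure) and two composites of mortality with hospitalisation, all at 6 months. That is four bullets, or six outcomes (1 + 3 + 2).

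**Analysis.** Section 12.10 rules out imputation. The visible text of section 12 gives no day-180 cut-off and no censoring rule for these endpoints.

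**The concern.** The missed-visit rule suits a study with several follow-up visits, where a subject absent from one can be picked up at the next. Here, failing to keep the schedule and missing the visit are the same event. The wording puts that event both inside and outside the lost-to-follow-up category, and the remedy it offers is a later visit that is not scheduled.

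A dead or hospitalised subject cannot attend, so non-attendance is plausibly related to the outcomes being counted. Section 6.11 itself expects some patients not to complete the study procedures. If nobody is required to find out what happened to them, the reported 6-month figures may rest mainly on those who came. Attenders, for their part, are watched for anything from 150 to 210 days under a single 6-month label.

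**Working it through.** The plan gives no figure to reproduce for these endpoints: they have no stated sizing, and the sample size, alpha, responder rates and dropout rate are redacted. The event risks, spread of visit dates and non-attendance fractions below are assumptions.

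**1. Window (section 6.7).** Earliest on-time exit: 180 − 30 = day 150. Latest: 180 + 30 = day 210. A day-150 attender lacks 30/180 = 16.7% of the intended period. A subject seen on days 180–210 is covered to day 180.

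**2. Extremes under constant hazard.** If p is the risk by day 180, the risk by day t is 1 − (1 − p)^(t/180).

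| Assumed p | All seen day 150 | All seen day 210 |
|---|---|---|
| 5% | 1 − 0.95^(150/180) = 4.2% | 1 − 0.95^(210/180) = 5.8% |
| 10% | 8.4% | 11.6% |
| 20% | 17.0% | 22.9% |

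**3. Visits spread evenly over days 150–210.** Half are early, by 15 days on average, so the mean shortfall is 0.5 × 15 = 7.5 days (7.5/180 = 4.2%). A crude count to each subject's visit gives about 5.0% for a true 5%, because early and late visits offset. Counting the same subjects' events only to day 180, with no censoring adjustment, gives 4.8%.

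**4. Unknown status.** Let m be the fraction with unknown status and q the observed risk in the rest. The lower bound, with all unknowns event-free, is (1 − m)q. The upper bound, with all having the event, is (1 − m)q + m. With q = 5%:

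| m | Lower bound | Upper bound |
|---|---|---|
| 10% | 0.90 × 5% = 4.5% | 4.5% + 10% = 14.5% |
| 20% | 0.80 × 5% = 4.0% | 4.0% + 20% = 24.0% |

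These are limits, not predictions. They show that unresolved non-attendance can outweigh the visit window.

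**5. Is a status check required anywhere?** The contact steps in 6.12 aim at compliance with the visit, not at vital status or admissions. The 24-hour limits in 8.2 and 8.3.1 run from the site becoming aware of the event; they do not oblige the site to look. Unscheduled visits (6.8) are tied to changes in MPP programming and carry no planned activity. No visible step requires the check.

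**The case against.** A reader might infer that 6-month mortality and hospitalisation are simply not ascertained to 6 months, or that non-attenders are released from all follow-up and can never be withdrawn. The documents do not support that.

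- Subjects seen on days 180–210 are covered to day 180. The shortfall among attenders is confined to those seen on days 150–179 and is at most 30 days.
- Section 6.12 lets the investigator withdraw a subject at any time with reasonable rationale and lists non-compliance as a reason. A non-attender who is not withdrawn stays under surveillance by 8.2, which favours capture.
- Section 6.12 also states: "Site personnel should at all times make all reasonable efforts to locate and communicate with the subject". Section 7.2 requires non-attendance to be reported as a deviation, section 6.11 has sponsor personnel ensure completion of follow-up, and central monitoring (section 10) looks for missing data. Deaths and serious adverse events, including in-patient admissions that meet that definition, are reportable independently of the 6-month visit.
- The parenthesis can be read as separating one missed appointment from lost contact. The text is therefore better called self-contradictory than an exemption.
- It is tempting to call these the main safety outcomes. They are secondary endpoints; safety is handled through section 8. The visible hypotheses concern responders and the substudy, and with a single arm no between-arm contrast can be biased.
- Sections 12.1–12.3 are partly redacted, section 12.7 refers to a statistical analysis plan, and the content of Appendix E is not shown. A censoring rule could exist out of sight.

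All of this limits the claim. What remains is that the safeguards depend on a site learning of an event, and that the one procedure meant for a silent subject has no clear starting point. The deviation report records that the visit did not happen, not whether the subject is alive or was admitted.

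**Conclusion.** The point holds in limited form. Ascertainment to day 180 of the secondary mortality, hospitalisation and composite endpoints is not assured for subjects who miss the only scheduled follow-up visit or who are seen on days 150–179. Section 6.12 contradicts itself in a single-follow-up study, and no visible text requires a status check or states how unequal follow-up is handled.

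The visit window alone is probably a small problem. The 4.2% and 5.8% figures require every visit to fall at one edge of the window, and a spread of dates largely offsets in a crude count. Non-attendance may be the larger issue, but its size cannot be stated because the dropout rate is redacted. All figures rest on the assumed risks, constant hazard and assumed fractions shown. The matter deserves correction because the rule cannot work as written and the repair is cheap. A missing 6-month echocardiogram for the primary endpoint is a separate question.

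**What to change.** **Section 6.12.** Keep the statement that a late attender is not excluded. Reword the parenthesis and the Note so that any subject with no 6-month visit by day 210 enters the existing two-calls-plus-letter procedure. Require that this contact, or hospital records, document vital status and hospitalisations to day 180 before the Termination form is completed.

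**Section 4.4.2 and section 12.** Count events from implant to day 180 only, censoring at last contact if earlier. Use Kaplan-Meier at day 180 for mortality and the composites, and events per person-time for hospitalisation.

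Censoring deals with early attenders in the analysis. Full ascertainment for them would need a status check by telephone or records at or after day 180. For non-attenders, censoring does not replace the status check, because their absence may itself be related to the outcome.

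**Cost.** Protocol wording, a few extra calls or record checks, and slightly more analysis work. The calls and letter are already described.
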